9.1.7. Visit 7/ Day 45 (± 3 Day) Repeat Dose Period

- Obtain vital signs
- Review and update concomitant medications

- Review and assessment of AEs and SAEs
- Perform symptom-directed PE
- Obtain blood samples (prior to administration of G03-52-01 or Placebo) for the following:
 - PK
 - MNA
 - ADA
 - Clinical safety labs
 - Hypersensitivity panel
 - Future use (if consent given)
- Distribute reactogenicity diary
- Obtain pregnancy test
- Obtain urine dipsticks
- Obtain urine sample for toxicology
- Perform Breathalyzer test to detect recent alcohol use
- Counsel women of child-bearing potential on the avoidance of pregnancy
- Counsel the subject not to receive any botulinum toxin preparation (e.g., Botox) for 4 months after injection
- Counsel the subject on eligibility to receive any authorized COVID-19 vaccine 8 days after visit

Administration of repeat 50 mg or 100 mg G03-52-01 dose or placebo IM injection. Subjects will be observed at the study site for approximately 1 hour after dose administration.

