- Chemistry panel that will include serum creatinine, BUN, calcium, total bilirubin, alkaline phosphatase, ALT, AST, sodium, potassium, albumin, PT, PTT, INR, total CK, carbon dioxide, and chloride. Subjects should be fasting for the chemistry panel.
- A CBC with differential will be obtained including WBC, RBC, hemoglobin, hematocrit, platelet count, MCV, MCH, MCHC, RDW, MPV, neutrophils, lymphocytes, monocytes, eosinophils, and basophils.
- A serum pregnancy test will be obtained at screening for all women of reproductive capacity. A urine pregnancy test will be obtained and must be resulted prior to Day 1 dosing. Results must be confirmed as negative before study product is dosed.
- Urine drug screening.
- A urine dipstick will be done to evaluate for presence of protein, glucose or blood in urine. If dipstick is abnormal (>+1), a complete urinalysis with microscopic will be performed.
- A 12-lead ECG will be done during screening. Subjects with a QTc interval >450 milliseconds will be excluded from participation.
- Viral Serology includes HIV, HBsAg and antibody to HCV.
- Serum from subjects who give consent will be stored for future use.
- The Hypersensitivity Panel includes cytokine and complement panels, IgE, and tryptase. Refer to lab manual for further processing instructions. .
- PK samples will be collected for all subjects at pre-dose, 24 hours and 72 hours post dose, and on Days 8, 15, 45 (before repeat-dose or placebo), 49, 90, and 120.
- Serological samples (PD) will be collected for all subjects at pre-dose, 24 hours post dose, and on Days 8, 15, 45 (before repeat-dose or placebo), 49, 90, and 120.
- ADA samples will be collected and tested for all subjects at pre-dose and Days 15, 45 (before repeat-dose or placebo), 60, 90, 120, 150, 180, and 240.
- Samples to be collected pre-dose prior to Day 45 repeat dose.
- Subjects will be provided a reactivity diary prior to leaving the clinic on baseline/dosing Day 1. Subjects will be asked to complete daily diary records study Day 1-7 and diary is to be collected by site staff on Day 8 for review. Subjects will be provided a reactivity diary prior to leaving the clinic on baseline/dosing Day 45. Subjects will be asked to complete daily diary records study Day 46-52 and diary is to be collected by site staff on Day 60 for review.

Table 3: Schedule of Assessments (Cohort 4)

Study Visit	Screening ¹	Baseline/ Dosing ²		3	4	5	6	7	8	9	10	Unscheduled
		D 1	8-Hour Stay									

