**Table 3: Derived Variables**

Variable	Formula
Demographic and Baseline Characteristics	
Body Mass Index	weight (kg) / [height (m)] 
Age	Calculated at the time of informed consent. Sample SAS code to calculate age is: age = floor((informed consent date - date of birth)/365.25)
Baseline	Baseline is defined as the last measurement prior to the first treatment administration
Derivation of Durations	
Study day at any visit	date of visit – date of first dose. One day is added if the difference is ≥ 0.
Duration of any events	end date of event – start date of event + 1
Other Derivations	
Incidence in a group	The proportion of the participants experiencing the outcome of interest compared to the total number of participants at risk of experiencing the outcome of interest. (e.g., the incident rate of SAEs after injection are the number of participants with an SAE reported after injection divided by the number of participants that received the injection).
Pharmacodynamic (PD) Parameters	
AUC (0-t)	Area under the concentration time-curve from the time of dosing to the time of the last measurable (positive) concentration
C max	Maximum observed concentration, occurring at time T max .
T max	Time of maximum observed concentration. For non-steady-state data, the entire curve is considered. If the maximum observed concentration is not unique, then the first maximum is used.
t 1/2	Terminal half-life defined as ln(2)/ λ z as measured during steady-state
Pharmacokinetic (PK) Parameters	

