## Statistical Analysis Plan (SAP)

---

study visit. AEs with a start date after subjects' final scheduled study visit will not be included in table summaries. All AEs captured in the database will be included in subject listings.

All AEs with the exception of reactogenicity events will be classified by Primary System Organ Class (SOC) and Preferred Term (PT) according to the Medical Dictionary for Regulatory Activities (MedDRA®) version 25.0. All AEs that occur after the initiation of study medication will be included in TFL summaries. Table summaries will include the frequency and percentage of subjects experiencing each event, as well as the total number of events experienced at each level of summarization (i.e., SOC and PT within SOC). The following summaries will be presented for all AEs, medically attended adverse events (MAAEs), and serious adverse events (SAEs) by SOC and PT and by treatment group and for all subjects:

- Overall (i.e., regardless of severity or relationship to treatment)
- By maximum severity grade (mild, moderate, or severe)
- By closest relationship to study medication

Additionally, an overall summary irrespective of SOC/PT categorization will be presented separately for all AEs with the exception of reactogenicity events. This overall summary will tabulate the number of subjects and events for: AEs, MAAEs, Grade 3 or greater AEs, AEs related to IP (possibly related or definitely related), Grade 3 or greater AEs related to IP (possibly related or definitely related), AEs with outcome of death, SAEs, SAEs related to IP (possibly related or definitely related), AEs leading to study discontinuation, AEs leading to discontinuation of IP, and AEs related to IP that led to discontinuation of IP.

Furthermore, a separate table will summarize the frequency and percentage of subjects experiencing each reactogenicity event and the total number of events experienced per term. The summary will be broken down by dose (i.e., Dose 1 and Dose 2) for Cohorts 1-3. Events that occur on or after date of first dose and before date of second dose will be summarized under Dose 1. Events that occur on or after date of second dose will be summarized under Dose 2. Reactogenicity events will be broken down into local reactions (injection site pain, injection site tenderness, injection site redness, injection site swelling) and systemic reactions (fever, headache, myalgia, abdominal pain, anorexia, nausea, vomiting, diarrhea, and malaise/fatigue).

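### The Dose 1 diary includes the injection day and the Dose 2 diary does not, so the by-dose reactogenicity table rests on unequal solicitation and is likely to understate Dose 2 rates.

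*Protocol*

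**What the plan says.** Footnote 19 of Table 2 in Protocol Appendix A sets both diary periods for Cohorts 1-3. After the first dose: "Subjects will be asked to complete daily diary records study Day 1-7". After the second: "Subjects will be asked to complete daily diary records study Day 46-52". The second diary is provided "prior to leaving the clinic on baseline/dosing Day 45". SAP Appendix A, footnote 19, repeats both periods.

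Study days count from the first dose. SAP Table 3 subtracts the date of first dose and then states "One day is added if the difference is ≥ 0", so Day 1 is the first injection day. Protocol 9.1.7 places the second injection at "Visit 7/ Day 45 (± 3 Day) Repeat Dose Period".

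SAP 9.10.1 plans one reactogenicity table: "The summary will be broken down by dose (i.e., Dose 1 and Dose 2) for Cohorts 1-3". Its allocation rule for the second dose is "Events that occur on or after date of second dose will be summarized under Dose 2". The same section leaves reactogenicity events out of the system organ class and preferred term coding and out of the overall adverse event summary. The by-dose table is therefore the only tabulation it names for them.

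**The concern.** Safety and tolerability of repeat dosing is the first primary objective, and this table is where a reader will look to see whether the second injection is tolerated as well as the first. The two columns do not rest on the same question to the subject. After Dose 1 the subject is asked about the day of the injection; after Dose 2 the questions start the next day. The allocation rule counts events on the second dosing date under Dose 2, so the table has a place for reactions that the diary instruction does not ask about.

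A short-lived reaction that begins and ends on the injection day is solicited once and not the second time. A lower Dose 2 rate could then reflect real tolerability, the missing day, or both, and nothing in the planned table would separate them.

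**Working it through.** The plan gives no rate or power figure for this point, so there is nothing to reproduce. The check converts study days to post-dose days (study day minus dosing day) and compares coverage.

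**Nominal dosing**

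- Dose 1 on Day 1: Days 1-7 minus 1 = post-dose days 0-6.
- Dose 2 on Day 45: Days 46-52 minus 45 = post-dose days 1-7.
- Common to both: days 1-6. Dose 1 alone has day 0; Dose 2 alone has day 7.

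**Dosing off Day 45.** The visit window allows Day 42 to Day 48. The documents do not say whether Day 46-52 moves with the actual dose. If it does, every subject has days 1-7. If it is fixed, and the diary is available only from the dosing visit, the coverage is:

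| Dose 2 given on | Post-dose days covered | Days within 0-6 |
|---|---|---|
| Day 42 | 4-10 | 3 |
| Day 43 | 3-9 | 4 |
| Day 44 | 2-8 | 5 |
| Day 45 | 1-7 | 6 |
| Day 46 | 0-6 | 7 |
| Day 47 | 0-5 | 6 |
| Day 48 | 0-4 | 5 |

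On the fixed reading, only a Day 46 dose matches the Dose 1 coverage, and days 1-6 are not common to all subjects.

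**Direction.** Assume equal true risk after both doses and capture by diary only. Let f be the share of reactions starting on the injection day, r the chance that such a reaction lasts into the next day, and g the share first appearing on post-dose day 7. For a Day 45 dose:

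- Dose 1 capture = 1 − g
- Dose 2 capture = 1 − f(1 − r)

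Dose 2 is understated whenever f(1 − r) > g, that is, when reactions confined to day 0 outnumber those first seen on day 7. Protocol 3.3.1 places fever, chills and rigors after antibody injection mostly in the first two hours, which favours that direction for systemic reactions. It says nothing about how long local reactions last.

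**Sensitivity only.** None of these inputs is in the documents. Take f and r each between 0.3 and 0.7, with later onsets halving daily to day 7, so that g = (1 − f)/127.

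- f = 0.3, r = 0.7: Dose 2 = 1 − 0.3 × 0.3 = 0.91; Dose 1 = 1 − 0.7/127 = 0.994; ratio 0.92.
- f = 0.7, r = 0.3: Dose 2 = 1 − 0.7 × 0.7 = 0.51; Dose 1 = 1 − 0.3/127 = 0.998; ratio 0.51.

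The width of this range shows how far the answer depends on unknown inputs.

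**Other routes of capture.** Both doses have about one hour of clinic observation. Dose 1 is followed by visits at 24 and 72 hours and diary collection on Day 8. Dose 2 is followed by a visit on Day 49 (± 3 days) and diary collection on Day 60. The back-up is thinner after the dose whose diary omits the injection day.

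**The case against.** The strongest reply is that not asking is not the same as not recording. The second diary is in the subject's hands on Day 45, adverse events are reviewed that day and at Visit 8, and the schedules mark diary review at Days 45 and 49. The SAP allocates by event date and does not limit the table to diary entries, so a recorded Day 45 reaction would be counted under Dose 2. This stands as a reason to check the data first. It does not restore balance, because Dose 1 has the same observation hour, closer visits and a diary that asks about the day.

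Second, the table is descriptive. No test between doses is planned, and the interim safety comparison is between cohorts. That is correct and limits the consequence. All arms use the same Dose 2 diary, so active against placebo within Dose 2 is not distorted in this way, though absolute Dose 2 rates would still be low.

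Third, the SAP appendix is weak corroboration, since its footnote 13 still carries storage days that the protocol has removed. The protocol's own footnote is sufficient.

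A reader might also infer that a subject dosed on Day 48 would have diary days before the injection in the Dose 2 column. The documents do not support this: the diary is handed out at the dosing visit, and the SAP already places events before the second dose under Dose 1. No exclusion rule for pre-dose days is needed.

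**Conclusion.** The asymmetry is real and stands in the current text. If the diaries were completed as instructed, injection-day reactions were solicited after Dose 1 and not after a Day 45 Dose 2. The likely direction is understatement of Dose 2, provided that reactions confined to day 0 outnumber those first seen on day 7 and that other routes do not make up the loss.

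A reader might go further and read a definite bias, with a size, into the Dose 1 and Dose 2 columns. The documents do not support that. They give no reaction rates, no durations and no diary form, and they do not show whether Day 45 entries were made. The ratios in the working are conditional on assumptions and should not be carried into a report as an estimate. Protocol 3.3.1 also says that these injection reactions are more likely at a first exposure, so a lower Dose 2 rate could be partly genuine. The planned table cannot tell the two apart.

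This should be put right before the final analysis. It affects a primary tolerability display but no planned test.

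**What to change.** Cohorts 1-3 have completed their last visit (Protocol 3.1.3), so the remedy lies in SAP 9.10.1 and its table shells.

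1. Check, before the final analysis, whether diary entries exist for the actual Dose 2 date, and report for how many subjects.
2. If they do, present both doses over post-dose days 0-6, counted from the actual dosing date.
3. If they do not, keep the planned table and add a by-dose display limited to the post-dose days that both diaries cover, counted from the actual dosing date: days 1-6 for a Day 45 dose. Show Dose 1 day 0 separately, and footnote that Dose 2 day 0 was not solicited. If only some subjects have such entries, this is the safer route.
4. In either case, report the number of post-dose diary days covered for subjects dosed off Day 45.

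The cost is a data check, a few lines of SAP text, one extra display and a footnote. The downside is that the common-window display leaves out the Dose 1 injection day, which is why day 0 is shown alongside and the planned table is kept.

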APPENDIX C. INTRAMUSCULAR (IM) INJECTION ADMINISTRATION

G03-52-01 or placebo will be administered via IM injections on Days 1 and 45 for Cohorts 1-3 and on Days 1 for Cohort 4.

Please refer to the Pharmacy Manual for additional dose preparation and administration detail.

APPENDIX D. SUMMARY OF CHANGES

Table 4: Summary of Changes for Version 4.0

Version 3.0	Version 4.0	Reason for Change

PROTOCOL TITLE: A Phase 2, Randomized, Double-Blinded, Placebo-Controlled Study to Evaluate the Safety, Tolerability, Pharmacodynamics, and Immunogenicity of a Repeat Dose of G03-52-01 in Adult Subjects
	
PROTOCOL TITLE: A Phase 2, Randomized, Double-Blinded, Placebo-Controlled Study to Evaluate the Safety, Tolerability, Pharmacodynamics, and Immunogenicity of G03-52-01 in Adult Subjects
	
Addition of Cohort 4 (single dose of G03-52-01)

Name of Sponsor/Company: Ology Bioservices, Inc.
	
Name of Sponsor/Company: Resilience Government Services, Inc.
	
Resilience Government Services, (previously Ology Bioservices) updated

ICON Medical Monitor: ██████████ ██████████
	
ICON Medical Monitor: ██████████ ██████████
	
New medical monitor

Deltoid
	
Deltoid muscle
	
Clarification on the administration of injection in the deltoid muscle

Page 19: Protocol Synopsis, Subject Participation
 
Each subject’s participation in the study is approximately 254 days (up to a 14-day screening, 1-hour inpatient stay and 240 days outpatient follow-up)
	
Page 15: Protocol Synopsis, Subject Participation
 
Subject’s participation Cohorts 1-3 of in the study is approximately 254 days (up to a 14-day screening, 1-hour inpatient stay and 240 days outpatient follow-up)
 
Subject’s participation in Cohort 4 is approximately 134 days (up to a 14-day screening, 8-hour inpatient stay and 120 days outpatient follow-up)
	
Addition of Cohort 4


Page 19: Protocol Synopsis, Objectives and Endpoints
 
Primary Objectives:
 
 • To evaluate the safety and tolerability of repeat intramuscular (IM) administration of G03-52-01 in healthy adult subjects • Demonstrate target protective concentration (NAC) value of BoNT/A and BoNT/B through Day 45 and Day 90 • To evaluate lot-to-lot variability of the two doses of G03-52-01 	
Page 15-16: Protocol Synopsis, Objectives and Endpoints
 
Primary Objectives:
 
 • To evaluate the safety and tolerability of single or repeat intramuscular (IM) administration of G03-52-01 in healthy adult subjects • Cohorts 1-3 
 ○ Demonstrate target protective concentration (NAC) value of BoNT/A and BoNT/B through Day 45 and Day 90 	
Addition of Cohort 4 and new objectives and endpoints

Primary Endpoints:
 
 • The occurrence of adverse events (AEs) and serious adverse events (SAEs) following administration of G03-52-01 to the final visit • The occurrence of changes from baseline in physical examination (PE), vital signs, and clinical safety laboratory values following administration of G03-52-01 to the final follow-up visit • To evaluate target protective concentration (NAC) value > 0.02 U/mL (botulinum neurotoxin [BoNT]/A) or > 0.03 U/mL (BoNT/B) at Day 45 and Day 90 	
 ○ To evaluate lot-to-lot variability of the two doses of G03-52-01 ○ For Cohort 4, demonstrate target protective concentration (NAC) value of BoNT/A and BoNT/B at 4 and 8 hours post dose 
Primary Endpoints:
 
 • The occurrence of adverse events (AEs) and serious adverse events (SAEs) following administration of G03-52-01 to the final visit • The occurrence of changes from baseline in physical examination (PE), vital signs, and clinical safety laboratory values following administration of G03-52-01 to the final follow-up visit • For Cohorts 1-3, to evaluate target protective concentration (NAC) value > 0.02 U/mL (botulinum neurotoxin [BoNT]/A) or > 0.03 U/mL (BoNT/B) at Day 45 and Day 90 • For Cohort 4, to evaluate the proportion of subjects with target protective concentration (NAC) value > 0.02 U/mL (botulinum neurotoxin [BoNT]/A) or > 0.03 U/mL (BoNT/B) at 4 and 8 hours post dose 	

Page 19: Protocol Synopsis, Objectives and Endpoints
 
Secondary Objectives:
 
 • Demonstrate target protective concentration (NAC) value of BoNT/A and BoNT/B through Day 120 • Pharmacodynamic (PD) and anti-drug antibody (ADA) at pre-dose through the end of study 
Secondary Endpoints:
	
Page 16: Protocol Synopsis, Objectives and Endpoints
 
Secondary Objectives:
 
 • Cohorts 1-3 
 ○ Demonstrate target protective concentration (NAC) value of BoNT/A and BoNT/B through Day 120 ○ To evaluate pharmacodynamic (PD) and anti-drug antibody (ADA) at 	
Addition of Cohort 4 and new objectives and endpoints

 • To evaluate target protective concentration (NAC) value > 0.02 U/mL (BoNT/A) or > 0.03 U/mL (BoNT/B) at Day 120 • Descriptive statistics of selected PD and ADA at all-time points tested 	
pre-dose through the end of study
 
 • Cohort 4 
 ○ Demonstrate target protective concentration (NAC) value of BoNT/A and BoNT/B at 2 hours post dose ○ To assess pharmacokinetics (PK) at pre-dose through end of study ○ To evaluate pharmacodynamic (PD) and anti-drug antibody (ADA) at pre-dose through the end of study 
Secondary Endpoints:
 
 • Cohorts 1-3 
 ○ To evaluate the proportion of subjects with target protective concentration (NAC) value > 0.02 U/mL (BoNT/A) or > 0.03 U/mL (BoNT/B) at Day 120 ○ Descriptive statistics of selected PD and ADA at all-time points tested • Cohort 4 
 ○ To evaluate the proportion of subjects with target protective concentration (NAC) value > 0.02 U/mL (botulinum neurotoxin [BoNT]/A) or > 0.03 U/mL (BoNT/B) at 2 hours post dose ○ PK analysis at the determined timepoints ○ Descriptive statistics of determined PD and ADA timepoints 	

Page 19-20: Protocol Synopsis, Objectives and Endpoints
	
Page 16: Protocol Synopsis, Objectives and Endpoints
	
Addition of Cohort 4 and new objectives and endpoints


Exploratory Objectives:
 
 To evaluate pharmacokinetic (PK) parameters to ensure ADA evaluation adequate of the two lots 
Exploratory Endpoints:
 
 Descriptive statistics of selected PK parameters at all time points tested of the two lots 	
Exploratory Objectives:
 
 For Cohorts 1-3, to evaluate pharmacokinetic (PK) parameters to ensure ADA evaluation adequate of the two lots 
Exploratory Endpoints:
 
 For Cohorts 1-3, descriptive statistics of selected PK parameters at all time points tested of the two lots 	

Page 20: Protocol Synopsis, Methodology
 
This study is a Phase 2, multicenter, randomized, double-blinded, placebo-controlled study to evaluate the safety, tolerability, PD, and immunogenicity of a repeat dose (50 mg and 100 mg) of G03-52-01 administered by IM injection(s) in adult subjects.
 
Approximately 375 subjects will be enrolled in this study. No formal sample size calculations will be performed for this Phase 2 study, as there is no planned formal hypothesis testing, and the target enrollment of 375 subjects was based on previous experiences from studies conducted with similar products. Subjects will be randomized 2:2:1 to the following concurrent cohorts:
 
 Cohort 1: 50-mg dose of G03-52-01 on Day 1 and repeat 50-mg dose on Day 45 (N=150) Cohort 2: 100-mg dose of G03-52-01 on Day 1 and repeat 100-mg dose on Day 45 (N=150) Cohort 3: Placebo on Day 1 and placebo on Day 45 (N=75) 
Subjects who receive 50 mg dose of G03-52-01, 100 mg dose of G03-52-01, or placebo on Day 1 will receive a repeat injection of the same dose on Day 45. Within Cohorts 1 and 2, subjects will be randomized 1:1 to Lot 1 or Lot 2 of each respective dose.
	
Page 16-17: Protocol Synopsis, Methodology
 
This study is a Phase 2, multicenter, randomized, double-blinded, placebo-controlled study to evaluate the safety, tolerability, PD, and immunogenicity of a repeat dose (50 mg and 100 mg) or single dose (100 mg) of G03-52-01 administered by IM injection(s) in adult subjects.
 
Approximately 625 subjects will be enrolled in this study. No formal sample size calculations will be performed for this Phase 2 study, as there is no planned formal hypothesis testing, and the target enrollment of subjects was based on previous experiences from studies conducted with similar products. Subjects will be randomized 2:2:1 to the following cohorts 1-3:
 
 Cohort 1: 50-mg dose of G03-52-01 on Day 1 and repeat 50-mg dose on Day 45 (N=150) Cohort 2: 100-mg dose of G03-52-01 on Day 1 and repeat 100-mg dose on Day 45 (N=150) Cohort 3: Placebo on Day 1 and placebo on Day 45 (N=75) 
Subjects in Cohort 4 will be randomized in a 4:1 to receive a single 100 mg dose of G03-52-01 or Placebo on Day 1 (n=250).
 
Subjects who receive 50 mg dose of G03-52-01, 100 mg dose of G03-52-01, or placebo on Day 1 will receive a repeat injection of the same dose on
	
Updates to study design to support addition of Cohort 4 and new objectives/endpoints


	
Day 45 for Cohorts 1-3. Within Cohorts 1 and 2, subjects will be randomized 1:1 to Lot 1 or Lot 2 of each respective dose. Subjects in Cohort 4 will be randomized 4:1 to receive G03-52-01 (Lot #C2300157) or Placebo.
	

Page 21: Protocol Synopsis, Methodology
 
The study will include up to 14-day screening period and an approximately 1-hour stay in the clinic after dosing is complete on Day 1 and Day 45 for PK assessment and to ensure that no hypersensitivities or safety signals occur. Follow-up visits will occur 24 hours and 72 hours post dose, and on Days 8, 15, 45, 49, 60, 90, 120, 150, 180, and 240.
 
Safety labs will be drawn at pre-dose, 24 hours post dose, and on Days 15, 45 (before repeat-dose or placebo), 60, 120, and 240.
 
Subjects within each dose lot and placebo cohort will be randomized 2:1 to contribute PD or PK samples according to the following schedules.
 
PD samples will be tested by the Battelle Mouse Neutralization Assay (MNA) for serotypes A and B at pre-dose, 24 hours post dose, and on Days 8, 15, 45 (before repeat-dose), 49, 90, and 120. The first 25 subjects randomized for each drug product (DP) lot of 50 mg and 100 mg doses and placebo will be tested at all 8 timepoints. The remaining samples from the subjects who received either dose or lot of G03-52-01 (including placebo) will only be tested using MNA at pre-dose and Days 45, 90, and 120.
 
PK samples will be tested by electrochemiluminescence assay (ECLA) or enzyme-linked immunosorbent assay (ELISA) at pre-dose, 24 hours and 72 hours post dose, and on Days 8, 15, 45 (before repeat-dose), 49, 90, and 120. A total of 25 subjects for each DP lot of 50 mg and 100 mg doses and placebo will be tested at all timepoints.
	
Page 17-18: Protocol Synopsis, Methodology
 
The study will include up to 14-day screening period and an approximately 1-hour stay in the clinic after dosing is complete on Day 1 and Day 45 for subjects in Cohorts 1-3 for PK assessment and to ensure that no hypersensitivities or safety signals occur. Follow-up visits will occur 24 hours and 72 hours post dose, and on Days 8, 15, 45, 49, 60, 90, 120, 150, 180, and 240 for Cohorts 1-3.
 
Cohort 4 subjects will have an 8 hour stay at the clinic after dosing for safety, PD, and PK assessment. and safety follow up. Follow-up visits will occur at 24 hours, 72 hours, and on Days 8, 15, 30, 45, 90, and 120.
 
Safety labs will be drawn at pre-dose, 24 hours post dose, and on Days 15, 45 (before repeat-dose or placebo), 60, 120, and 240 for Cohorts 1-3.
 
Subjects in Cohort 4 will have safety labs drawn at screening and Day 15, 45, and 120.
 
For Cohorts 1-3, subjects within each dose lot and placebo cohort will be randomized 2:1 to contribute PD or PK samples according to the following schedules for Cohorts 1-3:
 
PD samples will be tested by the Battelle Mouse Neutralization Assay (MNA) for serotypes A and B at pre-dose, 24 hours post dose, and on Days 8, 15, 45 (before repeat-dose), 49, 90, and 120. The first 25 subjects randomized for each drug product (DP) lot of 50 mg and 100 mg doses and placebo will be tested at all 8 timepoints. The remaining samples from the subjects who received either dose or lot of G03-52-01 (including placebo) will only be tested using
	
Updates to study design to support addition of Cohort 4 and new objectives/endpoints



ADA samples will be tested at pre-dose and Days 15, 45 (before repeat-dose or placebo), 60, 90, 120, 150, 180, and 240 on all study subjects.
 
An interim Clinical Study Report (CSR) is planned for the first 125 subjects through Day 120.
	
MNA at pre-dose and Days 45, 90, and 120.
 
PK samples will be tested by electrochemiluminescence assay (ECLA) or enzyme-linked immunosorbent assay (ELISA) at pre-dose, 24 hours and 72 hours post dose, and on Days 8, 15, 45 (before repeat-dose), 49, 90, and 120. A total of 25 subjects for each DP lot of 50 mg and 100 mg doses and placebo will be tested at all timepoints.
 
For Cohort 4, PK and PD samples will be tested for the first 30 subjects who receive active drug and complete sample collection at 24 hours. PD samples will be tested by the Battelle Mouse Neutralization Assay (MNA) for serotypes A and B at pre-dose, 2 hours, 4 hours, 8 hours, 24 hours and on Days 30, and 45 and 90. PK samples will be tested by electrochemiluminescence assay (ECLA) or enzyme-linked immunosorbent assay (ELISA) at pre-dose, 2 hours, 4 hours, 8 hours, 24 hours, 72 hours post dose, and on Days 8, 15, 30, 45, 90, and 120. ADA samples will be tested at pre-dose and Days 15, 45 (before repeat-dose or placebo), 60, 90, 120, 150, 180, and 240 for study subjects in Cohorts 1-3; and at pre-dose and post-dose on Days 90 and 120 for Cohort 4.
 
An interim Clinical Study Report (CSR) is planned for the first 125 subjects in Cohorts 1-3 through Day 120.
	

Page 21: Protocol Synopsis, Study Population
 
375 healthy male and female subjects between the ages of 18 and 65 years of age
	
Page 18: Protocol Synopsis, Study Population
 
625 healthy male and female subjects between the ages of 18 and 65 years of age
	
Addition of Cohort 4 (n=250 subjects)

Page 21: Protocol Synopsis, Inclusion Criteria
 
8. The urine drug screen is negative
	
Page 18: Protocol Synopsis, Inclusion Criteria
 
8. The urine drug screen is negative.
 
 • For Cohorts 1-3, if a subject has a positive urine drug screen that the PI believes is caused by 	
Clarification on drug screening and inclusion criteria

	
a currently prescribed medication (except for THC) the PI may enroll the subject if they meet all inclusion criteria, and none of the exclusion criteria.
 
 For Cohort 4, If a subject has a positive urine drug screen that the PI believes is caused by a currently prescribed medication or positive for THC, the PI may enroll the subject if they meet all other inclusion criteria and none of the exclusion criteria. 	

Page 22: Protocol Synopsis, Inclusion Criteria
 
11. Agrees not to participate in vigorous activity 2 days prior to dosing and 2 days post-dose Day 1 and Day 45, per Investigator discretion.
	
Page 18: Protocol Synopsis, Inclusion Criteria
 
11. Agrees not to participate in vigorous activity 2 days prior to dosing and 2 days post-dose Day 1 and Day 45 for Cohorts 1-3 and Day 1 for Cohort 4, per Investigator discretion.
	
Clarification on vigorous activity

Page 23: Protocol Synopsis, Exclusion Criteria
 
15. Use of H1 antihistamines or beta-blockers within 5 days of dosing Day 1 and Day 45 (PRN use could be allowed with MM approval).
	
Page 19: Protocol Synopsis, Exclusion Criteria
 
15. Use of H1 antihistamines or beta-blockers within 5 days of dosing Day 1 and Day 45 for Cohorts 1-3 and Day 1 for Cohort 4 (PRN use could be allowed with MM approval).
	
Clarification on use of H1 antihistamines or betablockers

Page 23: Protocol Synopsis, Test Product, Dose and Mode of administration
 
G03-52-01 DP is a mixture of five human monoclonal immunoglobulin G (IgG)1 antibodies (NX01, NX11, XB10, XB18, and XB23) and one humanized monoclonal IgG1 antibody (NX02) which bind to non-overlapping epitopes on BoNT/A/B.
 
 Two DP lots (DP Lots #274-190416 and #279-190722) will be supplied. 
All subjects will receive a 50 mg or 100 mg G03-52-01 injection or equal volume of placebo in the central,
	
Page 20: Protocol Synopsis, Test Product, Dose and Mode of administration
 
G03-52-01 DP is a mixture of five human monoclonal immunoglobulin G (IgG)1 antibodies (NX01, NX11, XB10, XB18, and XB23) and one humanized monoclonal IgG1 antibody (NX02) which bind to non-overlapping epitopes on BoNT/A/B.
 
 Two DP lots (DP Lots #274-190416 and #279-190722) will be supplied for Cohorts 1-3. One DP lot (DP Lot #C2300157) for Cohort 4. 	
Addition of Cohort 4 and new DP lot


thickest portion of the deltoid on Study Day 1 and Day 45.
	
Subjects in Cohorts 1-3 will receive a 50 mg or 100 mg G03-52-01 injection or equal volume of placebo in the central, thickest portion of the deltoid on Study Day 1 and Day 45.
 
Subjects in Cohort 4 will receive a single 100 mg G03-52-01 or equal volume of placebo in the central, thickest portion of the deltoid on Study Day 1.
	

Page 25: General Information Central Laboratory for Safety Testing (Cohorts 1-3): ██████████
	
Page 22: General Information Central Laboratory for Safety Testing (Cohorts 1-3): ██████████ Central Laboratory for Safety Testing (Cohort 4): ICON Laboratory Services
	
New central laboratory for safety testing of Cohort 4 samples

Page 28: Currently Available Treatments, G03-52-01 Development G03-52-01 drug product (DP) is being investigated to prevent (pre-exposure) and reduce the incidence or progression of disease following exposure to BoNT/A and /B in adults.
	
Page 25: Currently Available Treatments, G03-52-01 Development G03-52-01 drug product (DP) is being investigated for pre-exposure and post-exposure prophylaxis of botulism from BoNT/A and/or BoNT/B in adults.
	
Update to include pre-exposure and post-exposure prophylaxis

Page 28: Currently Available Treatments, G03-52-01 Development The safety and pharmacokinetics (PK) of G03-52-01 are currently being evaluated in a Phase 1 clinical study of a single IM injection of G03-52-01 conducted by Ology Bioservices (Ology Bio). To date, there are no safety concerns with the administration of the DP (G03-52-01).
	
Page 26: Currently Available Treatments, G03-52-01 Development The safety and pharmacokinetics (PK) of G03-52-01 were evaluated in a Phase 1 clinical study of a single IM injection of G03-52-01 conducted by Resilience Government Services (RGS). There were no safety concerns with the administration of the DP. All subjects in Cohorts 1-3 of the Phase 2 clinical study completed their last subject visit. All available safety data was reviewed by the DSMB and no safety concerns were identified.
	
Updates to include available Phase 1 clinical data


Page 29-30: Rationale For Use of G03-52-01 The ongoing Phase 1 clinical trial is evaluating the safety and tolerability of a single IM injection of G03-52-01 administered to healthy adults. Sentinel dosing occurred within each cohort as described in the full protocol (G03-52-001.001). The starting dose in the clinical trial was 10 mg, which was escalated to 25 mg, 50 mg, and 100 mg with no safety concerns identified.
	
Page 27: Rationale For Use of G03-52-01 The Phase 1 clinical trial evaluated the safety and tolerability of a single IM injection of G03-52-01 administered to healthy adults. Sentinel dosing occurred within each cohort as described in the full protocol (G03-52-001.001). The starting dose in the clinical trial was 10 mg, which was escalated to 25 mg, 50 mg, and 100 mg with no safety concerns identified.
	
Updates to include available Phase 1 clinical data

Based on the Day 60 and Day 120 interim analysis, G03-52-01 was safe and well tolerated in Cohorts 1-3. To date, Cohort 4 did not show safety concerns and the product was well tolerated.
 
The nonclinical Investigational New Drug (IND)-enabling toxicology studies were designed to support this clinical design, including the dose levels and IM route of administration. Based on the potency of the G03-52-01 lots manufactured to date, the doses evaluated are anticipated to support PK analyses with serum drug concentrations in the range for the prevention (pre-exposure) and reduction of the incidence or progression of botulism from BoNT/A and/or BONT/B .
	
G03-52-01 was safe and well tolerated in all subjects who participated in the Phase 1 study and in the Phase 2 study to date.
 
The nonclinical Investigational New Drug (IND)-enabling toxicology studies were designed to support this clinical design, including the dose levels and IM route of administration. Based on the potency of the G03-52-01 lots manufactured to date, the doses evaluated are anticipated to support PK analyses with serum drug concentrations in the range for pre-exposure and post-exposure prophylaxis of botulism from BoNT/A and/or BoNT/B.
	

Page 32: Study Objectives
 
Primary Objectives:
 
 • To evaluate the safety and tolerability of repeat intramuscular (IM) administration of G03-52-01 in healthy adult subjects • Demonstrate target protective concentration (NAC) value of BoNT/A and BoNT/B through Day 45 and Day 90 • To evaluate lot-to-lot variability of the two doses of G03-52-01 
Secondary Objectives:
 
 • Demonstrate target protective concentration (NAC) value of BoNT/A and BoNT/B through Day 120 • Pharmacodynamic (PD) and anti-drug antibody (ADA) at pre-dose through the end of study 
Exploratory Objectives:
 
 • To evaluate PK parameters to ensure ADA evaluation adequate of the two lots 	
Page 29: Study Objectives
 
Primary Objectives:
 
 • To evaluate the safety and tolerability of single or repeat intramuscular (IM) administration of G03-52-01 in healthy adult subjects • Cohorts 1-3 
 ○ Demonstrate target protective concentration (NAC) value of BoNT/A and BoNT/B through Day 45 and Day 90 ○ To evaluate lot-to-lot variability of the two doses of G03-52-01 ○ For Cohort 4, demonstrate target protective concentration (NAC) value of BoNT/A and BoNT/B at 4 and 8 hours post dose 
Secondary Objectives:
 
 • Cohorts 1-3 
 ○ Demonstrate target protective concentration (NAC) value of BoNT/A and BoNT/B through Day 120 	
Addition of Cohort 4 and new objectives

	
 ○ To evaluate pharmacodynamic (PD) and anti-drug antibody (ADA) at pre-dose through the end of study ● Cohort 4 
 ○ Demonstrate target protective concentration (NAC) value of BoNT/A and BoNT/B at 2 hours post dose ○ To assess pharmacokinetics (PK) at pre-dose through end of study ○ To evaluate pharmacodynamic (PD) and anti-drug antibody (ADA) at pre-dose through the end of study 
Exploratory Objectives:
 
 ● For Cohorts 1-3, to evaluate PK parameters to ensure ADA evaluation adequate of the two lots 	

Page 32: Study Outcome Measures
 
Primary Endpoints:
 
 ● The occurrence of adverse events (AEs) and serious adverse events (SAEs) following administration of G03-52-01 to the final visit ● The occurrence of changes from baseline in physical examination (PE), vital signs, and clinical safety laboratory values following administration of G03-52-01 to the final follow-up visit ● To evaluate target protective concentration (NAC) value > 0.02 U/mL (botulinum neurotoxin [BoNT]/A) or > 0.03 U/mL (BoNT/B) at Day 45 and Day 90 
Secondary Endpoints:
 
 ● To evaluate target protective concentration (NAC) value > 	
Page 29-30: Study Outcome Measures
 
Primary Endpoints:
 
 ● The occurrence of adverse events (AEs) and serious adverse events (SAEs) following administration of G03-52-01 to the final visit ● The occurrence of changes from baseline in physical examination (PE), vital signs, and clinical safety laboratory values following administration of G03-52-01 to the final follow-up visit ● For Cohorts 1-3, to evaluate target protective concentration (NAC) value > 0.02 U/mL (botulinum neurotoxin [BoNT]/A) or > 0.03 U/mL (BoNT/B) at Day 45 and Day 90 ● For Cohort 4, to evaluate the proportion of subjects with target protective concentration 	
Addition of Cohort 4 and new endpoints

